4. OTHER SENSITIVITY, SUPPORTIVE AND EXPLORATORY ANALYSES FOR THE PRIMARY EFFICACY ENDPOINT

This section relates to Section 4.7.1.2 of version 1 of the SAP dated 08 July 2016.

Time-to-event analyses as done for the primary analysis will be carried out at 1-year and 2-year landmarks for the intent-to-treat (ITT) Population. For each landmark, the log-rank test, stratified by stratification variables at randomization (cardiovascular [CV] risk category, use of ezetimibe, and geographical region [Westernized, Eastern European, and Asia Pacific countries]), will be used to compare the time-to-event between treatment groups. Similarly, hazard ratios and 95% confidence intervals will be determined using Cox proportional hazards modelling. Patients without events prior to the landmark time will be censored.

For the recurrent CV events analyses based on 5-component Major Adverse Cardiovascular Events (MACE) (CV death, non-fatal myocardial infarction [MI], non-fatal stroke, unstable angina requiring hospitalization, or coronary revascularization), in addition to the Anderson and Gill and the Li and Lagakos methods specified in the SAP dated 08 July 2016, the total CV event counts will be analyzed using a Negative Binomial Model ([Rogers 2012](#), [Rogers 2014](#), and [Claggett 2018](#)). It will be implemented using SAS Proc Genmod with a log link function, log exposure time as offset, and treatment group and randomization strata as factors.

As additional sensitivity analysis for the primary composite endpoint will be carried out, namely, an on-treatment analysis which includes primary event onset up to 0 and 30-days after permanent discontinuation of study drug.

All SAP Addendum efficacy analyses are considered exploratory and are not included in the formal SAP testing scheme.

5. ANALYSIS OF SECONDARY EFFICACY ENDPOINTS

This section relates to Section 4.7.3 of version 1 of the SAP dated 08 July 2016.

As done for the primary analysis, time-to-event analyses will be carried out at 1-year and 2-year landmarks for the key secondary endpoints for the ITT Population.

6. ANALYSIS OF TERTIARY ENDPOINTS

This section relates to Section 4.7.4 of version 1 of the SAP dated 08 July 2016.

The following clinical events that are positively adjudicated by the Clinical Endpoint Committee (CEC) will be analyzed as tertiary endpoints for the ITT Population:

- Composite of total mortality, or new congestive heart failure (CHF)
- Composite of CV death, or new CHF
- Sudden cardiac death
- Peripheral artery disease (PAD)
- Atrial fibrillation, or atrial flutter

These tertiary endpoints will be analysed similarly as for the primary composite endpoint.

In addition, the following will be analysed as tertiary endpoints for the ITT Population:

- Relationship between on-treatment high-sensitivity C-reactive protein (hsCRP) and the primary and key secondary endpoints
- Relationship between on-treatment serum eicosapentaenoic acid (EPA) and the primary and key secondary endpoints

To assess the relationship between on-treatment hsCRP and the primary and key secondary endpoints, subgroup analyses will be carried out as done for the ITT population for patients grouped according to values greater or equal to or less than 2 mg/dL at baseline and at 2 years.

To assess the relationship between on-treatment serum EPA and the primary and key secondary endpoints, Kaplan-Meier (KM) curves will be produced for AMR101 treated patients grouped into tertiles based on their values at year 1 and will be compared with the placebo-treated patients.

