Kaplan-Meier estimates will be used to summarize the time to the first event of the composite endpoint. Event probabilities at 6-month intervals and the median time to event (if estimable) will be presented. The log-rank test, stratified by stratification variables at randomization (CV risk category, use of ezetimibe, and geographical region [Westernized, Eastern European, and Asia Pacific countries]), will be used to compare the time-to-event between treatment groups. The two-sided alpha level for the primary analysis will be reduced from 0.05 to account for the interim analyses based on a group sequential design with O'Brien-Fleming boundaries generated using the Lan-DeMets alpha-spending function.

The hazard ratio (HR) comparing the two treatment groups along with a confidence interval (CI) adjusted for the interim analyses and p-value will be calculated from a stratified Cox proportional hazards (PH) model with treatment as the only covariate, and stratified by CV risk category at baseline, use of ezetimibe at baseline, and geographical region (Westernized, Eastern European, and Asia Pacific countries). Kaplan-Meier curves stratified by each of the stratification variables will be presented.

The primary efficacy analysis will be performed on the ITT population. A corresponding sensitivity analysis will be performed using the mITT and PP populations.

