For measurements of lipids, lipoproteins, and inflammatory markers, the change from baseline and the percent change will be summarized at each visit. Since these parameters are typically not normally distributed, the Wilcoxon rank-sum test will be used for treatment comparisons of the percent change from baseline, and medians and quartiles will be provided for each treatment group. The medians of the differences between the treatment groups and 95% CIs will be estimated with the Hodges-Lehman method. In addition, shift-tables may be generated as appropriate.

As an additional exploratory analysis, the relationship between post-baseline biomarker values and treatment effects with the primary and key secondary composite endpoints will be assessed by adding biomarker values (for example, at 4 month, or at 1 year, etc.) as time-dependent covariates in the Cox proportional hazards model. Diagnostic plots for the proportional hazards assumption will be evaluated.

Weight is measured at the screening visit and at all follow-up visits, including the last visit of the study. Waist circumference will be measured at the randomization visit (Visit 2; Day 0), Visit 5 (Day 720) and the last visit of the study. Descriptive statistics will be presented by visit and treatment group for baseline, post-treatment change from baseline, and the percent change from baseline. Analysis methods for repeated measurements will be used to compare percent change from baseline between treatments.

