4.7.5 Exploratory Analysis of Subgroups

Analyses of the effects of patients off study drug and withdrawn from study have on primary endpoint will be performed.

Subgroup analyses of the primary and key secondary endpoints will be performed as described for the primary endpoint. For each subgroup, Kaplan-Meier estimates, the log-rank test stratified by stratification factors used at randomization (except where the subgroup is a stratification factor), and HRs and CIs from the Cox proportional hazards model as specified for the primary efficacy endpoint, will be summarized by treatment group.

The following subgroups will be explored:

Demographic Parameters:

- gender;
- age (<65 years and \geq 65 years);
- race (white and non-white, or any other subset with at least 10% of the total number of patients);
- geography (Westernized, Eastern European, and Asia Pacific countries); and

- baseline ezetimibe use (yes/no).

Disease Parameters:

- CV risk category;
- the presence/absence of diabetes at baseline; and
- renal dysfunction (estimated glomerular filtration rate [eGFR] <60 mL/min/1.73m²) using the Chronic Kidney Disease Epidemiology Collaboration (CKD-EPI) equation as follows:

$$eGFR = 141 \times \min(S_{cr}/\kappa, 1)^\alpha \times \max(S_{cr}/\kappa, 1)^{-1.209} \times 0.993^{\text{Age}} \times 1.018 \text{ [if female]} \times 1.159 \text{ [if black]}$$

Where:

S_{cr} is serum creatinine in mg/dL,
 κ is 0.7 for females and 0.9 for males,
 α is -0.329 for females and -0.411 for males,
 min indicates the minimum of S_{cr}/κ or 1, and
 max indicates the maximum of S_{cr}/κ or 1.

Treatment Parameters:

- statin intensity at baseline (statin type and regimen)

Statin intensity categories as defined in ACC/AHA Cholesterol Guidelines (Stone 2013) and patient's 10-year CV Risk Score (Goff 2013) will be considered.

Baseline Lipid and Lipoprotein Parameters:

- LDL-C (by tertile);
- HDL-C (by tertile, and tertile by gender);
- TG (by tertile, and tertile by gender);
- RLP-C (by tertile);
- TG \geq 150 mg/dL and TG <150 mg/dL;
- TG \geq 200 mg/dL and TG <200 mg/dL;
- TG \geq median, TG < median;
- combined highest tertile for TG and lowest tertile for HDL-C;
- gender-specific highest tertile for TG and lowest tertile for HDL-C;

- TG \geq 200 mg/dL with HDL-C \leq 35 mg/dL;
- hs-CRP (\leq 3 mg/L and $>$ 3 mg/L) and by gender;
- hs-CRP (\leq 2 mg/L and $>$ 2 mg/L) and by gender;
- Apo B (by tertile); and
- non-HDL-C (by tertile).

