Adjustment for Baseline TG Level: Following a protocol amendment, dated May 2013, only patients with qualifying TG \geq 200 mg/dL were enrolled in the study. Prior to this, patients with qualifying TG levels as low as approximately 135 mg/dL were enrolled. In order to account and adjust for the fact the follow-up times may be different depending on the baseline TG level, a Cox PH model as mentioned above but additionally with baseline TG as a covariate will be fitted to the data at each interim. Diagnostic plots for the PH assumption will be evaluated.

The consistency of the treatment effects in subgroups will be assessed for the primary and key secondary efficacy endpoints. For each subgroup variable, a Cox proportional hazards model with terms for treatment, stratification factors (with the exception of those subgroup variables related to the stratification factors, i.e., CV risk category), subgroup, and treatment-by-subgroup interaction will be performed. The main treatment effect will not be tested with this model. P-values for testing the interaction terms $<$ 0.15 will be considered significant. Results will be presented in a Forest plot.

All subgroup analyses will be conducted for the ITT, mITT and PP populations.

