7. EXPLORATORY ANALYSIS OF SUBGROUPS

This section relates to Section 4.7.5 of version 1 of the SAP dated 08 July 2016.

The following will be added to the subgroup analyses:

- Baseline Hemoglobin A1c (HbA1c) value (<6.5%, ≥6.5%)

- Baseline PAD
- Baseline triglyceride (TG) levels ≥ 150 mg/dL with high-density lipoprotein cholesterol (HDL-C) levels ≤ 40 mg/dL for males and ≤ 50 mg/dL for females

Subgroup analyses of the primary and key secondary endpoints will be performed as described for the primary endpoint. For each subgroup, Kaplan-Meier estimates, the log-rank test stratified by stratification factors used at randomization (except where the subgroup is a stratification factor), and hazard ratios (HRs) and confidence intervals (CIs) from the Cox proportional hazards model as specified for the primary efficacy endpoint, will be summarized by treatment group.

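### The SAP Addendum's 2-year hsCRP analysis compares AMR101 with placebo inside groups formed after randomization, so the method it names does not test the hsCRP–outcome relationship it sets out to assess

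*Combined protocol and SAP*

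**What the plan says.** SAP Addendum Section 6 adds to the tertiary analyses the "Relationship between on-treatment high-sensitivity C-reactive protein (hsCRP) and the primary and key secondary endpoints". The method it names is that "subgroup analyses will be carried out as done for the ITT population for patients grouped according to values". The cut is set at 2 mg/dL, applied once to the baseline measurement and once to the 2-year measurement. The section gives no model, tested contrast or time origin for this analysis.

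What a subgroup analysis delivers is defined elsewhere. Addendum Section 7 and SAP 4.7.5 list Kaplan-Meier estimates, a stratified log-rank test, and hazard ratios with confidence intervals "from the Cox proportional hazards model as specified for the primary efficacy endpoint, will be summarized by treatment group". SAP 4.7.1.1 says that this hazard ratio comes from a "stratified Cox proportional hazards (PH) model with treatment as the only covariate", with time counted from randomization.

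Two other provisions bear on the question. SAP 4.7.5 adds a consistency model with terms for treatment, the stratification factors, "subgroup, and treatment-by-subgroup interaction will be performed"; its only significance rule is for the interaction, at 0.15. SAP 4.7.4 enters post-baseline biomarker values "as time-dependent covariates in the Cox proportional hazards model", and hs-CRP is on its biomarker list.

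After randomization, hs-CRP is scheduled only at Visit 5 (Day 720) and at the Last Visit (Protocol 6.1.2.3, 6.1.2.5 and Appendix A). Addendum Sections 2 and 4 class these analyses as exploratory, but Section 2 commits them to the clinical study report.

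**The concern.** The aim concerns a biomarker and an outcome. The named test concerns a drug and an outcome, within levels of the biomarker. A log-rank test inside the high-hsCRP group asks whether AMR101 differs from placebo there. It does not ask whether patients with high hsCRP have more events.

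Two further problems apply to the 2-year grouping but not to the baseline one. First, hsCRP at 2 years is measured after randomization. If AMR101 changes hsCRP, and the same risk factors drive both hsCRP and events, the arms are no longer comparable within a group. Second, if time runs from randomization as in the primary analysis, a nonfatal event before Day 720 is counted in a group defined afterwards, while patients who died earlier cannot be classified at all.

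At stake is the reading of a result that will appear in the clinical study report: a treatment contrast, possibly biased, under a label that promises an hsCRP–outcome relationship.

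**Working it through.** **1. Calibration on the plan's own figure.** The documents give no figure for the hsCRP analysis, so the design inputs were checked first. Inputs: hazard ratio 0.85 and 1612 events (Protocol 12.3); Z bounds 2.669, 2.289 and 2.031 at 967, 1290 and 1612 events (iSAP Table 1).

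- Drift at full information: |ln 0.85| × √(1612/4) = 0.1625 × 20.07 = 3.263.
- Fixed-design power: Φ(3.263 − 1.96) = 0.904.
- Three-look power from the multivariate normal distribution: 0.8972, with one-sided alpha 0.0250. The iSAP states 0.897 and 0.025. Reproduced.

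**2. Events before and after the sample.** Inputs: N = 7990, control hazard 0.053, hazard ratio 0.85, the stated accrual pattern, 6.5 years, no dropout. Expected first primary events are 1601, of which 855 fall after a patient's second year. The difference is 746, and 746/1601 = 47%. This is an upper bound on the events that could be placed in a later-defined group, because patients who died before Day 720 have no sample.

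**3. What the within-group test responds to.** 1000 simulated trials per row, two-sided 5%. Assumptions not in the documents: 7000 patients at risk at year 2, half with high hsCRP, 2.6 further years of follow-up, control hazard 0.053 in the low group. Only events after year 2 are counted.

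| Treatment HR | hsCRP HR | Treatment test, high group | Treatment test, low group | Test of hsCRP term |
|---|---|---|---|---|
| 1 | 1.0 | 5.9% | 5.1% | 4.9% |
| 1 | 1.5 | 5.6% | 5.6% | 100% |
| 1 | 2.0 | 4.0% | 4.7% | 100% |
| 0.85 | 1.0 | 36.8% | 36.8% | 5.9% |

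The simulation standard error at 5% is √(0.05 × 0.95/1000) = 0.7 percentage points, so the treatment columns in the first three rows do not differ from 5%. They do not move with the hsCRP association. The last column does.

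**4. Bias from grouping after randomization.** Illustrative simulation of 300 trials with 7000 patients and no treatment effect on events. A standard normal risk factor U sets the hazard at 0.045 × exp(0.5U). A patient is in the high group if 0.8U + 0.6 × noise − 0.3 × (AMR101) exceeds 0. The mean AMR101-to-placebo rate ratio was 1.068 in the high group and 1.074 in the low group, where the truth is 1. Both conditions are needed. When AMR101 lowered the share with high hsCRP by 10 percentage points but no shared risk factor was present (treatment HR 1, hsCRP HR 1.5), the within-group tests rejected in 3.5% and 5.8%.

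**5. Power of a direct test on the remaining events.** Power = Φ(|ln HR| × √(d·p·(1 − p)) − 1.96), with d = 855 and p the share with high hsCRP.

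- HR 1.2, p = 0.5: 0.1823 × √(855 × 0.25) = 2.666; power 76%.
- HR 1.2, p = 0.3: 0.1823 × √(855 × 0.21) = 2.443; power 69%.
- HR 1.5: about 100% at either share.

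**The case against.** The strongest reply is that the plan already answers the question elsewhere. The time-dependent model in SAP 4.7.4 makes hs-CRP a model term, and a Day 720 value used that way can bear only on later events. The Addendum adds to the SAP and does not replace it. If Section 6 means the whole SAP 4.7.5 package, the consistency model brings in an hsCRP main effect and a tested interaction, and the Kaplan-Meier estimates by group show the association descriptively. So a reader might infer that the plan cannot detect an hsCRP relationship at all; the documents do not support that. What remains is narrower. The 4.7.5 rule covers the interaction and not the hsCRP term. The SAP's own hs-CRP subgroups are baseline ones. The examples in 4.7.4 are 4 months and 1 year, when no hs-CRP sample is scheduled. Curves by 2-year group share the time-origin problem.

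A second tempting reading is that the 36.8% rejection under treatment HR 0.85 and no hsCRP effect is an inflated false-positive rate. It is not. It is the power of the treatment test against its own false null, and the Addendum sets no null or decision rule for hsCRP.

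Third, the SAP's related objective concerns post-baseline biomarkers and treatment effects. Read as shorthand for that, treatment hazard ratios by achieved hsCRP are on topic. That is a fair reading of the intent, but it leaves the post-randomization selection untouched.

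Finally, Section 6 does not itself name AMR101 against placebo. That contrast is inferred from SAP 4.7.1.1, SAP 4.7.5 and Addendum Section 7.

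**Conclusion.** The concern holds for the 2-year grouping. The within-group tests are uninformative about the hsCRP–outcome association, and the arm comparison is biased if AMR101 changes hsCRP and shared risk factors drive both. The bias of about 7% in step 4 only illustrates this: its direction and size depend on assumed inputs, and the documents give no effect of AMR101 on hsCRP in this trial. The missing time origin matters because nearly half of the expected events can precede the sample.

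It does not extend to the baseline hsCRP groups, where the comparison is randomized, nor to any primary or secondary conclusion. The result is exploratory, so the change is worth making because it is cheap and the output will be reported. The event counts assume no dropout and a complete set of Visit 5 samples, and they concern the primary endpoint; the documents give no event rate for the key secondary.

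**What to change.** Rewrite the hsCRP paragraph in Addendum Section 6 as follows.

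- For the 2-year analysis, start follow-up at Visit 5. Include patients still in follow-up, free of the endpoint in question, and with a Visit 5 hsCRP value.
- Fit the stratified Cox model with Visit 5 hsCRP as the tested term, once as continuous log(hsCRP) and once as the two groups. Adjust for treatment and baseline hsCRP, and add a treatment-by-hsCRP term.
- State how this aligns with the time-dependent model in SAP 4.7.4: the same hsCRP scale, the same adjustment, and the Day 720 value entering at its sampling date.
- Keep AMR101-versus-placebo subgroup hazard ratios for the baseline hsCRP groups only.

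The same sentence also needs its unit reconciled. It cuts at 2 mg/dL, which is 20 mg/L, while SAP 4.7.5 and the list of additional analyses use 2 mg/L.

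The cost is one paragraph and one model on data already scheduled. The downside is precision: with about 855 instead of 1601 events, standard errors are larger by a factor of about √(1601/855) = 1.37. Power stays high for a strong association and is moderate for a hazard ratio of 1.2.

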 - Ankle-brachial index (ABI) <0.9 with symptoms of intermittent claudication;
 - History of aorto-iliac or peripheral arterial intervention (catheter-based or surgical).

OR

CV Risk Category 2: defined as patients with:

1. Diabetes mellitus (Type 1 or Type 2) requiring treatment with medication AND
2. Men and women ≥ 50 years of age AND
3. One of the following at Visit 1 (additional risk factor for CVD):
 - Men ≥ 55 years of age and Women ≥ 65 years of age;
 - Cigarette smoker or stopped smoking within 3 months before Visit 1;
 - Hypertension (blood pressure ≥ 140 mmHg systolic OR ≥ 90 mmHg diastolic) or on antihypertensive medication;
 - HDL-C ≤ 40 mg/dL for men or ≤ 50 mg/dL for women;
 - Hs-CRP > 3.00 mg/L (0.3 mg/dL);
 - Renal dysfunction: Creatinine clearance (CrCL) > 30 and < 60 mL/min (> 0.50 and < 1.00 mL/sec);
 - Retinopathy, defined as any of the following: non-proliferative retinopathy, pre-proliferative retinopathy, proliferative retinopathy, maculopathy, advanced diabetic eye disease or a history of photocoagulation;
 - Micro- or macroalbuminuria. Microalbuminuria is defined as either a positive micral or other strip test (may be obtained from medical records), an albumin/creatinine ratio ≥ 2.5 mg/mmol or an albumin excretion rate on timed collection ≥ 20 mg/min all on at least two successive occasions; macroalbuminuria, defined as Albustix or other dipstick evidence of gross proteinuria, an albumin/creatinine ratio ≥ 25 mg/mmol or an albumin excretion rate on timed collection ≥ 200 mg/min all on at least two successive occasions;
 - ABI < 0.9 without symptoms of intermittent claudication (patients with ABI < 0.9 with symptoms of intermittent claudication are counted under CV Risk Category 1).

Note: Patients with diabetes and CVD as defined above are eligible based on the CVD requirements and will be counted under CV Risk Category 1. Only patients with diabetes and no documented CVD as defined above need at least one additional risk factor as listed, and will be counted under CV Risk Category 2.

4. Women may be enrolled if all 3 of the following criteria are met:
 - They are not pregnant;
 - They are not breastfeeding;

- They do not plan on becoming pregnant during the study.
5. Women of child-bearing potential must have a negative urine pregnancy test before randomization.
Note: Women are not considered to be of childbearing potential if they meet one of the following criteria as documented by the investigator:

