12.2.4.5. Exploratory Subgroup Analyses

Analyses of the effects that patients off study drug and withdrawn from study have on the primary endpoint will be performed.

Subgroup analyses of the primary and key secondary endpoints will be performed as described for the primary endpoint. For each subgroup, Kaplan-Meier estimates, the log-rank test stratified by stratification factors used at randomization (except where the subgroup is a stratification factor), and HRs and CIs from the Cox proportional hazards model as specified for the primary efficacy endpoint, will be summarized by treatment group.

The following subgroups will be explored:

Demographics:

- gender;
- age at baseline (<65 years and ≥65 years);
- race (white and nonwhite, or any other subset with at least 10% of the total number of patients);
- geographical region (Westernized, Eastern European, and Asia Pacific countries); and

- baseline ezetimibe use (yes/no).

Disease Parameters:

- CV risk category;
- the presence/absence of diabetes at baseline; and
- renal dysfunction at baseline (estimated glomerular filtration rate [eGFR] <60 mL/min/1.73m²) using the Chronic Kidney Disease Epidemiology Collaboration (CKD-EPI) equation as follows:

$$eGFR = 141 \times \min(S_{cr}/\kappa, 1)^\alpha \times \max(S_{cr}/\kappa, 1)^{-1.209} \times 0.993^{Age} \times 1.018 \text{ [if female]} \times 1.159 \text{ [if black]}$$

Where:

S_{cr} is serum creatinine in mg/dL,

κ is 0.7 for females and 0.9 for males,

α is -0.329 for females and -0.411 for males,

min indicates the minimum of S_{cr}/κ or 1, and

max indicates the maximum of S_{cr}/κ or 1 (Levey 2009).

Treatment Parameters:

- statin intensity at baseline (statin type and regimen)
Statin intensity categories as defined in ACC/AHA Cholesterol Guidelines (Stone 2013) and patient's 10-year CV Risk Score (Goff 2013).

Baseline Lipid and Lipoprotein Parameters:

- LDL-C (by tertile);
- HDL-C (by tertile, and tertile by gender);
- TG (by tertile, and tertile by gender);
- RLP-C (by tertile)
- TG ≥150 mg/dL and TG <150 mg/dL;
- TG ≥200 mg/dL and TG <200 mg/dL;
- TG ≥ median, TG < median;
- combined highest tertile for TG and lowest tertile for HDL-C;
- gender-specific highest tertile for TG and lowest tertile for HDL-C;
- TG ≥ 200 mg/dL with HDL-C ≤35 mg/dL;
- hs-CRP (≤3 mg/L and >3 mg/L) and by gender;
- hs-CRP (≤2 mg/L and >2 mg/L) and by gender;
- Apo B (by tertile); and
- non-HDL-C (by tertile).

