3. ADDITIONAL EXPLORATORY EFFICACY ANALYSES

The following list presents additional pre-specified exploratory efficacy analyses that could be of interest to the general clinical and scientific community:

- Non-fatal myocardial infarction (MI) (including both clinical manifestation and silent MI categorizations) – intent-to-treat (ITT) Population
- Evaluation of effect of time-weighted (or area under the curve [AUC]) eicosapentaenoic acid (EPA) data on the primary and key secondary composite endpoints – ITT Population
- Sensitivity analyses on the primary and key secondary composite endpoints by excluding elective coronary artery revascularizations if onset is <3 months post randomization; and also excluding peri-procedural MIs – ITT Population
- Two silent MI (SMI) sensitivity analyses on the primary and key secondary composite endpoints – ITT Population:
 - counting all potential SMIs identified by Clinical Endpoint Committee (CEC) electrocardiogram (ECG) reviewer, whether confirmed at final ECG or not; and,
 - counting only potential SMIs that have at least one confirmatory ECG showing persistence of Q-waves (even if not present at final ECG)
- Non-alcoholic fatty liver disease (NAFLD) analyses using NAFLD Fibrosis Score (NFS), assessing – ITT Population:
 - effect on primary and key secondary composite endpoints by baseline NFS category; and,
 - treatment effect on change from baseline in NFS at 1 and 5 years
- Individual and combined on-treatment goal achievement of triglyceride (TG) ≤ 150 mg/dL and hsCRP ≤ 2 mg/L at 2 years, and end of study – ITT Population
- Additional renal function (eGFR) analyses – ITT Population:
 - primary and key secondary composite endpoints for patients with baseline renal dysfunction [eGFR] ≥ 60 and < 90 mL/min/1.73m²

- treatment effect on change from baseline in renal function (eGFR) at 1 and 5 years
- Sensitivity analyses on the primary and key secondary composite endpoints by excluding patients with post-randomization low density lipoprotein cholesterol (LDL-C) values >100 mg/dL; and another for >70 mg/dL – ITT Population
- Analyses of hospitalization data (pooled positively adjudicated unstable angina requiring hospitalization, congestive heart failure [CHF] requiring hospitalization, and cardiac arrhythmia requiring hospitalization) – ITT Population
 - Time from randomization to first hospitalization
 - Recurrent event analysis on hospitalization

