4. ADDITIONAL EXPLORATORY SAFETY ANALYSES

The following list presents additional pre-specified exploratory safety analyses that could be of interest to the general clinical and scientific community:

- Number and percent of patients with the following liver function abnormalities – Safety Population:
 - Alanine aminotransferase (ALT) ≥ 3 x Upper Limit of Normal (ULN) + Total Bilirubin > 1.5 x ULN
 - ALT ≥ 5 x ULN
 - ALT ≥ 3 x ULN with an appearance of rash or worsening hepatitis symptoms
- Number and percent of patients with treatment-emergent cancer (overall, Lung Cancer, and Prostate Cancer) reported as adverse event (AE); each in 2 populations (ITT and hsCRP ≥ 2 mg/L) – Safety Population
- Number and percent of patients with treatment-emergent depression and social dysfunction reported as AE – Safety Population

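### SAP Addendum section 6 splits hsCRP at 2 mg/dL, which is 20 mg/L; every other cut at the value 2 is 2 mg/L, and the upper group would probably be too small to inform

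*Combined protocol and SAP*

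**What the plan says.** SAP Addendum section 6 adds the relationship between on-treatment hsCRP and outcome to the tertiary analyses. Its method is a subgroup analysis in the ITT population: "To assess the relationship between on-treatment hsCRP and the primary and key secondary endpoints", it takes "patients grouped according to values greater or equal to or less than 2 mg/dL at baseline and at 2 years".

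The other hsCRP thresholds in the documents are:

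- **Protocol inclusion criteria, CV Risk Category 2** (synopsis and section 4.1): above "3.00 mg/L (0.3 mg/dL"), stated in both units.
- **Protocol 12.2.4.5 and SAP 4.7.5, baseline subgroups:** a split at 3 mg/L and a second one, "hs-CRP (≤2 mg/L and >2 mg/L) and by gender".
- **SAP 4.7.1.2, covariate model:** a split at 3 mg/L.
- **PLAA section 3, on-treatment goal:** hsCRP at or below "2 mg/L at 2 years, and end of study".
- **PLAA section 4, cancer counts:** "each in 2 populations (ITT and hsCRP" at or above 2 mg/L).

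On the standing of the analysis, Addendum section 4 says: "All SAP Addendum efficacy analyses are considered exploratory and are not included in the formal SAP testing scheme". Addendum section 2 nevertheless commits its results to the clinical study report, whereas the PLAA analyses are optional.

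**The concern.** The Addendum's threshold carries the same digit as the other documents but a unit ten times larger, and nothing explains or justifies a cut at 20 mg/L. The PLAA and the Addendum bear the same date, and the PLAA uses 2 mg/L for the same marker at the same 2-year time.

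One committed analysis is at stake. The schedule of procedures collects hs-CRP at randomization, Visit 5 (Day 720) and the last visit, so the 2-year sample is the only routinely scheduled post-baseline value before study end. If the text is programmed literally, the split separates very few patients from the rest. If a programmer quietly uses mg/L instead, the output departs from the written plan, and SAP 4.3.1 requires such departures to be documented in the study report. If the unit is corrected after unblinding, the cut is no longer pre-specified.

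**Working it through.** **Step 1: unit check.** The factor is mg/dL × 10 = mg/L. It reproduces the protocol's own pair: 3.00 mg/L ÷ 10 = 0.3 mg/dL. Applied to the Addendum, 2 mg/dL × 10 = 20 mg/L, and 20 ÷ 2 = 10. This step uses the documents alone.

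**Step 2: share of patients above each cut.** The documents give no hsCRP distribution for this population. I assume a lognormal with median m from 1.5 to 4 mg/L and log-SD s from 0.9 to 1.3, used for both baseline and 2 years. Then P(hsCRP ≥ c) = 1 − Φ(ln(c/m)/s).

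For m = 2 and s = 1.1: ln(20/2)/1.1 = 2.303/1.1 = 2.093, so P = 1.8%, or about 145 of the planned 7990 patients.

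| m (mg/L) | s | at or above 20 mg/L | patients of 7990 | at or above 2 mg/L |
|---|---|---|---|---|
| 1.5 | 0.9 | 0.2% | 15 | 37.5% |
| 2 | 1.1 | 1.8% | 145 | 50.0% |
| 3 | 1.0 | 2.9% | 230 | 65.7% |
| 4 | 0.9 | 3.7% | 294 | 77.9% |
| 4 | 1.3 | 10.8% | 861 | 70.3% |

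Over the whole grid the range is 0.2% to 10.8% at 20 mg/L, and 37.5% to 77.9% at 2 mg/L. With the literal cut, 89.2% to 99.8% of patients are in the lower group.

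**Step 3: information in each group.** The design inputs are 1612 events, hazard ratio 0.85 and about 90% power (protocol 12.3). As a check, the Schoenfeld formula 4(z₀.₉₇₅ + z₀.₉₀)²/(ln 0.85)² gives 1592 events without interim looks. Power with 1612 events is 0.904 at two-sided 0.05, and 0.891 at the final one-sided level of 0.0211. The iSAP Table 1 power of 0.897 lies between these.

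I give each subgroup events in proportion to its share of patients, with power Φ(½√d·|ln 0.85| − 1.96).

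- **Upper group at 20 mg/L:** about 3 to 173 events, with power about 3% to 19%. At m = 2 and s = 1.1 there are 29 events: ½ × 5.385 × 0.1625 − 1.96 = −1.52, so power is 6.4%.
- **Smaller group at 2 mg/L:** power about 33% to 64%.

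**Step 4: precision.** The approximate 95% interval is HR × exp(±1.96 × 2/√d). For an estimate of 0.85:

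- 29 events: 2/√29 = 0.371, giving 0.41 to 1.76.
- 173 events, the most favourable case: 2/√173 = 0.152, giving 0.63 to 1.15.
- 806 events (half of 1612, the split at 2 mg/L when the median is 2): 2/√806 = 0.070, giving 0.74 to 0.98.

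**The case against.** **The analysis carries little weight.** It is exploratory and outside the formal testing scheme, and no primary, secondary or multiplicity result depends on it. This stands and limits the severity.

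**Much of the question is covered elsewhere.** The baseline split at 2 mg/L is already planned in the right unit (protocol 12.2.4.5, SAP 4.7.5). SAP 4.7.4 also enters post-baseline biomarkers, hs-CRP among them, in a Cox model as covariates that change over time, which needs no cut. This stands as partial cover. It does not replace the 2-year split that the Addendum commits to report.

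**A competent programmer would query the unit.** That is likely, but the plan should not depend on it.

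**Stronger readings that the documents do not support:**

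- A reader might infer that 2 mg/L is the only hsCRP cut used elsewhere. It is not: 3 mg/L appears in the eligibility criteria, the subgroup lists and the covariate model. What the documents have in common is the unit.
- A reader might infer that the analysis would come out null whatever the truth. A sparse upper group gives an imprecise hazard ratio, not a null one, and the lower group would track the overall treatment effect.
- A reader might take a near-empty upper group as established. It rests on an assumed distribution, and at the top of the range tried the group holds nearly 11% of patients.
- A reader might infer that adopting the SAP boundary (2 or less against more than 2) would make all the groups match. The PLAA itself puts exactly 2 in the lower group for its goal and in the upper group for its cancer counts.

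The Addendum also does not say how events before the 2-year measurement are handled in the 2-year grouping. Correcting the unit leaves that open.

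**Conclusion.** The point holds as a wrong unit in one committed exploratory analysis. The factor of ten is certain from the documents. That the intended cut was 2 mg/L is an inference, but a strong one, since no passage supports 20 mg/L.

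The consequence is probable, not certain. It rests on the lognormal assumption and on events falling in proportion to patients; if events are more frequent at high hsCRP, the upper group would have somewhat more of them. Across the range tried, the literal cut leaves one group with at most 19% power for the design hazard ratio and the other close to the whole ITT population, so the split could not do its job. At 2 mg/L both groups are large enough to give a usable estimate. Primary and secondary inference is untouched. The correction should be made, but the trial's conclusions do not turn on it.

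**What to change.** Before database lock and unblinding, change mg/dL to mg/L in the hsCRP grouping of SAP Addendum section 6, and record the change. The cost is one unit in one sentence. No data collection, sample size or testing rule changes.

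Optionally, in the same edit, state which group takes a value of exactly 2 mg/L and apply that across the SAP, the Addendum and both PLAA uses. Few patients would move, so this is a matter of consistency.
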